Selection and patient information: Patients in the COPD service; at the outset of their assessment, the end of PR and during maintenance sessions will be informed that the GENIE implementation evaluation is in progress.

Patients participating in these aspects of the service will be offered the opportunity to volunteer for the study, by the clinical team. If patients are interested they can then provide their names to the clinical staff to keep on a secure Solent database. Patient information sheets and invitation letters will be given out to the interested patients at their clinical visits to minimise postal and /or extra visits.

Once patients have received an information sheet, they will be allowed at least 72 hours to read and digest the information, (patient information sheets, consent and GP letters are separate documents), and share this with their friends and family if they wish to. Ideally, patients are provided with information in their clinical visits and are returning for clinical visits then appointments for research could be amalgamated with usual clinical visits. In this way extra study visits can be reduced. Patients, now participants, will be invited to consent and be randomised at the point of leaving usual clinical care. Furthermore, all patients at this point will have the opportunity to opt out of the study.

Once the participant is randomised (using block randomisation technique in clinic), then they will all receive normal clinical care (discharge planning with suggested activities), and the GENIE tool intervention, in the GENIE group, this is in addition to usual clinical care. Baseline questionnaires will also be administered at this visit.

The follow up period will commence 3 months (12 weeks) (+/- 1 week) from the day the GENIE tool was initially delivered. Participants will be invited back, via letter and /or phone call to attend their three month follow up visit at Bitterne Health Centre.

Solent NHS Trust will be the overall NHS organisation with one venue for study delivery; Bitterne Health Centre.

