Block randomisation technique, a commonly used technique in clinical trial design to reduce bias and achieve balance in the allocation of participants to treatment arms, especially in this case when the sample size is small (Efird, J. 2010). In order to reduce unconscious bias of the researcher, pre-prepared envelopes containing the possible combinations of group allocation, will be stored in a locked drawer in Bitterne Health Centre. The intention is to randomize in blocks of four, as this will complement the clinic structure. Therefore, each envelope will contain a pre-determined allocation pattern for that clinic (AABB, ABAB, BABA etc.).

The researcher team will share an excel spread sheet which will be set to generate a random number sequence. The next sequential number will be selected, which will then correspond to an envelope with the predetermined sequence. In this way the envelope selection is random, then sequence in the envelopes is also random, but ensures 50/50 grouping of participants. Baseline data for descriptive statistics will also be collected. (Data capture form appended)

In order to conduct meaningful analysis recruitment needs to reach at least 30 patients, in each group, however the maximum could be 60 in each group, 120 patients in total. Therefore recruitment could take between 6-9 months. The timeframe can be increased if necessary.

Initial / Baseline data collection:

Socio-economic data will be collected including; disease severity (FEV1), gender, EQ-5D, health care utilisation questionnaire, HEIQ and wellbeing questionnaires (CAT, GAD, PHQ-9), as well as an optional health behaviour questionnaire, from both the usual care group and the interventional group. Please note CAT, GAD, PHQ-9 FEV1 and gender are already captured routinely during clinical consultation.

Intervention

[figure not shown]
Assessment stratification and feedback:

Stage 1: The patient will complete a questionnaire online with the researcher/clinician. The patients will be asked to name the important people and activities in their network, type of relationship and frequency of contact using the concentric circles diagram.

Stage 2: The online process: consisting of series of questions will be used to elicit the participant's values and preferences for activities and support resources.

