Stage 3: This section will then link individuals to prioritised and valued activities and resources (links are to a pre-created database where local organisations and resources have been categorised).

Stage 4: The GENIE Tool then presents options in a user-friendly way, on a Google map with clear details about access, an example below:

Both groups will receive usual care, however one arm will have the addition of the intervention both will be called for a review at:

Three monthly follow up (+/- 1 week)

Six questionnaires will be administered. EQ-5D, health utilisation questionnaire, HEIQ and wellbeing questionnaires (CAT, GAD, PHQ-9), as well as the optional health behaviour questionnaire, so in 30 participants this will be seven, these will be repeated at 3 months post intervention (+/- 2 week). Furthermore, for those in the intervention arm, feedback and reflection discussions will be initiated using the network diagrams. Participants will be asked again for their permission to tape record these discussions to ensure parity and quality assurance between researchers.

Analysis of Outcomes

The study gathers data from the intervention arm and the non-intervention arm at baseline and 3 months post intervention. Results will be compared between the groups at baseline and 3 months post intervention. An economic analysis will be performed using a modified version of the Client Service Receipt Inventory (CSRI) (Beecham and Knapp 1999) Medication, health service use will be measured at baseline, 3 months post implementation and follow up. The modified version has been tailored to capture the needs of the target population (COPD patients). The CSRI has been widely used in previous research studies and has been evidenced as a valid measure of frequency of health service use (Patel 2005). The EQ5D is included to assess health status of patients during the GENIE intervention. Wellbeing score (CAT) and HEIQ and in the optional sub-group health behaviours (dietary intake, appetite, alcohol consumption and smoking habits) will be compared at baseline and 3 months. Furthermore, patient uptake of the social activities is to be recorded on paper using the Genie tool and compared between groups.

Rationale for the service implementation and evaluation design

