Following the training, the participants will be given the tools required to roll out the intervention

- Paper and web-based concentric circles with typologies and support suggestions
- Guidebook on how to deliver GENIE
- Access to the database and website

Identification, enrolment and randomisation

[figure not shown]

Table of Events

	Consent and Randomisation	Pre – intervention data collection	12 weeks post intervention data collection (+/- 1 week)	Potential 1 year follow up phase
Consent form discussion and taking informed consent	x			
Randomisation (Block)	x			
EQ-5D		X	x	x
Health Care Utilisation Questionnaire		X	x	x
Socio-economic background / demographic data		X		
Gender		X		
Disease severity (FEV1)		X		
HEIQ (Self-management)		X	x	
Optional Health behaviour questionnaire		x	x	x
CAT		X	x	x
Gad-7 /		X	x	
PHQ-9		x	x	x
Uptake discussion / online survey			x	x

Quality Assurance

The delivery of the intervention will be taped in as many cases as consented to ensure that the intervention is delivered consistently by the research team to all patients. The tape recording is for quality assurance, and is not intended for research utilisation or publication.

Future work

The participants included in this initial 3 months of the study could be followed up again in 1 year (12 months) to ascertain longer term outcomes and longevity of connections made. This element could consist of a paper or online survey to understand the uptake rates of the social actives 1 year on, and further investigation into QOL, **healthcare use and the option of assessing health behaviours.** All participants would be given the option of continuing for a year, and therefore those who continue would be decided by participant preference to remain in the study.

Analysis Plan

Primary Outcomes

Descriptive statistics of the cohort,

Descriptive statistics of the cohort will be reported including but not limited to; age, gender, severity of disease then the analysis will be broken down into 5 distinct sections;

- a) Pre and post intervention cost utility analysis for the usual care group and the intervention group.
- b) Comparative group - pre and post cost utility analysis; calculated cost per QALY (quality adjusted life years) gained and cost of healthcare usage per patient– usual care group at 3 months after leaving the COPD service compared with the post intervention group 3 (+/- 1 week) months after leaving the COPD service, with significance.

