- c) Clinical comparative analysis pre and post intervention including burden of disease (CAT score) and psychological impact of the disease, using Wilcoxin Ranked tests. Pre intervention burden of disease correlated with 3 months (+/- 1 week) disease burden post intervention (CAT), with significance.
- d) Clinical comparative analysis between groups at 3 months (as above) Wilcoxin Ranked tests.

12 month follow up survey

- a) Pre intervention burden of disease compared with 12 months disease burden post intervention (CAT).
- b) Activity uptake rates; recorded at 12 months post intervention, proportions of patients engaging in recommended activities.

Ethical Considerations

This is a new research trial of an existing social networking tool already used in long term diseases but not yet specifically in COPD. Prior to introducing this to the entire clinical service, clinical effectiveness recommends changes are trialled on a smaller proportion of the patient population in order to understand the benefits of time and cost prior to full scale implementation.

As this is an intervention within a clinical service and the evaluation is conducted with NHS participants, on NHS properties therefore University ERGO (Ethics) and HRA full NHS ethics application has been sort. The Ethical review number will be on all patient facing documentation. This ethical review has evaluated the social and scientific value of the study. Further to this it ensures adequacy of patient information, the informed consent process, recruitment arrangements and access to information.

The service implementation and evaluation will also be presented at the Solent Adult service line, clinical effectiveness and audit group for Solent NHS Trust approval.

References

Beecham, J. and Knapp, M. **Costing Psychiatric Interventions. Discussion paper.** Chapter for *Measuring Mental Health Needs*. 1999. Ed Thornicroft, G.

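### Item b) asks for cost per QALY gained with significance but gives no inferential method; a test of that ratio alone has no valid general form and should be replaced by net benefit with intervals

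*Combined protocol and SAP*

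**What the plan says.** In the Analysis Plan, under Primary Outcomes, item b) sets up the between-group economic comparison. The outputs are "calculated cost per QALY (quality adjusted life years) gained and cost of healthcare usage per patient", comparing usual care with GENIE at 3 months. The item closes with "months after leaving the COPD service, with significance". It does not say which quantity is to be tested, how, or at what level.

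No interval method, bootstrap, cost-effectiveness plane, net-benefit measure or willingness-to-pay threshold appears anywhere in the document. The only named tests are the Wilcoxon tests in items c) and d). Item d) reads "Clinical comparative analysis between groups at 3 months (as above) Wilcoxin Ranked tests".

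On size, the paragraph on recruitment after the randomisation description says "recruitment needs to reach at least 30 patients, in each group, however the maximum could be 60 in each group, 120 patients in total". No effect size, SD, alpha or power supports these numbers. Allocation is 1:1. Follow-up is at "3 months (12 weeks) (+/- 1 week) from the day the GENIE tool was initially delivered". The Analysis of Outcomes section says "The EQ5D is included to assess health status of patients during the GENIE intervention", with no value set, QALY formula or baseline adjustment.

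**The concern.** Cost per QALY gained is the cost difference divided by the QALY difference, and the denominator can fall on either side of zero. Two problems follow.

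- **Sign.** A negative ratio can mean cheaper and better, or dearer and worse. A positive ratio can mean dearer and better, or cheaper and worse. A p value on the ratio cannot tell these apart. This holds at any sample size.
- **Interval.** The 95% Fieller confidence set for a ratio is a bounded interval only when the denominator differs from zero at the 5% level. Otherwise the set is unbounded and no finite upper and lower limits can be reported.

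The trial's title makes cost effectiveness a main aim, and the Ethical Considerations section says benefits of time and cost are to be understood before full-scale implementation. If a significance statement were put on the ratio, the same number could be read in support of opposite service decisions.

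**Working it through.** **The plan's own figure.** The target of 30 to 60 per arm cannot be reproduced, because no alpha, power, effect or SD is stated. Solving backwards at two-sided 5% and 80% power, 30 per arm detects a standardised difference of about 0.72 and 60 per arm about 0.51.

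**Inputs from the document.** n = 30 or 60 per arm; 1:1 allocation; 12 weeks, so 12/52 = 0.231 year.

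**Assumptions (the document gives none of these).** EQ-5D SD 0.20 to 0.30; baseline to follow-up correlation ρ 0.5 to 0.7; EQ-5D gain at 12 weeks 0 to 0.10; no dropout, which favours the plan; two-sided 5%; normal approximation.

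**Formulas.** With QALYs by area under the curve, h = 0.231/2 = 0.1154.

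- QALY difference = h × d, where d is the EQ-5D difference at 12 weeks.
- Standard error, baseline-adjusted = h × SD × √(1−ρ²) × √(2/n).
- Standard error, unadjusted = h × SD × √(2(1+ρ)) × √(2/n).
- z = QALY difference / standard error.
- P(bounded Fieller interval) = Φ(z−1.96) + Φ(−z−1.96).
- P(QALY difference has the wrong sign) = Φ(−z).

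The factor h appears in both the difference and its standard error and cancels from z.

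**Worked case: d = 0.05, SD 0.25, ρ 0.6, adjusted.** The QALY difference is 0.1154 × 0.05 = 0.0058, and SD × √(1−ρ²) = 0.25 × 0.80 = 0.20.

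- 30 per arm: standard error 0.1154 × 0.20 × √(2/30) = 0.0060; z = 0.97; P(bounded) = 0.16. No bounded interval in 84% of trials; wrong sign in 17%.
- 60 per arm: standard error 0.0042; z = 1.37; P(bounded) = 0.28. No bounded interval in 72%; wrong sign in 9%.

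**Percentage of trials with no bounded 95% interval**, over SD 0.20 to 0.30 and ρ 0.5 to 0.7:

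| EQ-5D gain | Adjusted, 30/arm | Adjusted, 60/arm | Unadjusted, 30/arm | Unadjusted, 60/arm |
|---|---|---|---|---|
| 0 | 95 | 95 | 95 | 95 |
| 0.03 | 87-93 | 79-90 | 94 | 92-94 |
| 0.05 | 73-88 | 52-82 | 91-94 | 88-92 |
| 0.08 | 42-78 | 13-61 | 85-91 | 76-88 |
| 0.10 | 23-68 | 3-44 | 80-89 | 65-83 |

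At a gain of 0.05 with adjustment, the QALY difference has the wrong sign in 9-23% of trials (30 per arm) and 3-15% (60 per arm). An 80% chance of a significant QALY difference there would need 129 to 424 per arm.

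**Spread over quadrants.** This is a 5,000-trial simulation with assumed lognormal costs (mean £600, coefficient of variation 2), a true added cost of £50, an EQ-5D gain of 0.05, SD 0.25, ρ 0.6 and 30 per arm. Estimates fell 49% dearer and better, 35% cheaper and better, 7% cheaper and worse, and 9% dearer and worse. The ratio was therefore negative in 35 + 9 = 44% of trials and positive in 49 + 7 = 56%, with opposite conclusions inside each group.

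**The alternative.** Incremental net monetary benefit (threshold × QALY difference − cost difference) is a linear contrast, so its interval is always finite. At an assumed £20,000 per QALY, the 95% interval covered the true value in 95-96% of simulated trials at both sample sizes.

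**The case against.** The best case for the plan is that item b) is silent rather than wrong. Its closing request for significance covers a long sentence and may attach to healthcare cost per patient, where a test is ordinary, rather than to the ratio. That ambiguity stands, so the point applies only insofar as the ratio is what gets tested. The wording needs settling either way.

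Four stronger readings are tempting, and the documents do not support them.

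- **That the plan will use rank tests for costs.** A reader might infer this because Wilcoxon is the only named test. It is named only in c) and d), both labelled as clinical comparisons. Item b) names no test.
- **That the ratio will usually lack a finite interval whatever happens.** This depends on effect, SD and correlation, none of which the documents give. With baseline adjustment, 60 per arm and a gain of 0.08 to 0.10, a bounded interval exists in 39-97% of trials.
- **That the short follow-up causes the problem.** It makes the QALY difference small (0.0058 at a gain of 0.05), but it shrinks the standard error equally and cancels.
- **That the economic result cannot be interpreted.** Item b) also reports cost per patient, and EQ-5D and service use are collected in both arms at baseline and 12 weeks. Cost and QALY differences with ordinary intervals remain available. Only inference on the ratio by itself fails.

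**Conclusion.** The point holds in limited form. Item b) is a primary analysis that requests significance without a method, and one of its two outputs is a ratio for which no generally valid test exists. The sign ambiguity needs no assumptions. The unbounded-interval figures rest on the assumed EQ-5D SD, correlation and gain. They are severe for gains up to 0.05, and severe up to 0.10 if QALYs are not baseline-adjusted, which the plan does not mention. They ease considerably for a 0.10 gain with adjustment and 60 per arm. The quadrant percentages also depend on assumed costs. This should be fixed before analysis. It is a cheap improvement to the analysis plan and does not invalidate the trial.

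**What to change.** In item b), remove significance from cost per QALY and state what is reported instead:

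1. The between-arm difference in mean cost and in mean baseline-adjusted QALYs, each with a 95% bootstrap interval, resampling each patient's cost and QALY together within arm.
2. Incremental net monetary benefit with a 95% interval over a threshold range fixed in advance (for example £0 to £50,000 per QALY), and the probability that GENIE is cost-effective at each threshold.
3. Cost per QALY as a point estimate only, with its quadrant stated.

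This needs new wording and a few hours of programming, and no new data. The downside is that the economic result will look less decisive.

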The main aim here is to increase long term health care management options in Solent NHS Trust by building social capacity to support self-management. The GENIE tool will be introduced into the COPD service to improve options for social groups and exercise when leaving a pulmonary rehabilitation group, or when clinically unable to participate in exercise.

- to build social networking awareness and the importance of utilising existing social resources in the professional and voluntary members of the COPD service,
- to use social network mapping techniques and preference elicitation to engage COPD patients in reflecting on their support preferences and needs, help them access further resources and knowledge
- Evaluate the success of the social mapping techniques (GENIE) in the COPD patient population
- Evaluate the cost benefit to both to patients and to the health service of the GENIE in the COPD patient population

Objectives

Primary objectives

Compare and evaluate the health care utilisation and quality of life (burden of disease) in COPD patients using GENIE alongside usual care after leaving the COPD service with those offered only a current practice discharge plan.

Secondary objectives

Compare and evaluate the change in health behaviours, in particular diet and lifestyle in COPD patients using GENIE alongside usual care after leaving the COPD service with those offered only a current practice discharge plan.

Observe and understand the uptake and utilisation of the GENIE recommendations by COPD patients.

Explore social complexities in the COPD population.

Implementation Design

[figure not shown]
This protocol is concerned with the implementation and evaluation of the GENIE tool in the community facilitated by the COPD team and the subsequent evaluation of the GENIE in direct comparison to usual clinical practice.

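### The only between-arm clinical test states no baseline adjustment and is not named as decisive; the tests beside it do not compare GENIE with usual care

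*Combined protocol and SAP*

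**What the plan says.** The primary objective is comparative: "Compare and evaluate the health care utilisation and quality of life (burden of disease) in COPD patients using GENIE alongside usual care", set against patients who receive only the current discharge plan. Analysis of Outcomes adds "Results will be compared between the groups at baseline and 3 months post intervention" but names no test and no adjustment.

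The Analysis Plan, under Primary Outcomes, lists items a) to d). Items a) and b) are economic. The clinical ones are:

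- Item c), first sentence: "Clinical comparative analysis pre and post intervention including burden of disease (CAT score) and psychological impact of the disease, using Wilcoxin Ranked tests". No arm is named.
- Item c), second sentence: "Pre intervention burden of disease correlated with 3 months (+/- 1 week) disease burden post intervention (CAT), with significance".
- Item d): "Clinical comparative analysis between groups at 3 months (as above) Wilcoxin Ranked tests".

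No item is ranked above another. CAT, GAD-7 and PHQ-9 are collected at baseline "from both the usual care group and the interventional group" (Initial / Baseline data collection). On the questionnaires, Three monthly follow up says "these will be repeated at 3 months post intervention", and the Table of Events shows all three scores at both times. Planned recruitment is 30 to 60 per arm.

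**The concern.** Item d) is the clinical analysis that answers the objective, and two things about it are left open.

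First, it states no baseline term. Its bracketed cross-reference could mean the same measures as item c) or the same pre/post change, so the reader cannot tell whether baseline enters at all. If it does not, a small trial discards information that it already holds.

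Second, it has no stated priority over item c). Item a) reads "Pre and post intervention cost utility analysis for the usual care group and the intervention group", so the pre/post test in c) is most naturally read as run within each arm. Pooled over arms, it would not estimate the treatment contrast either. A within-arm change mixes any GENIE effect with whatever would have happened anyway. A correlation between two scores from the same person mainly shows that people who start high tend to stay high.

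No passage says that a significant result in c) will count as evidence for GENIE, but none rules it out. Risks / benefits ties offering the tool to all patients to a benefit seen in the intervention arm, and does not say that this must be a difference from usual care.

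**Working it through.** **Nothing to reproduce.** The target of 30 to 60 per arm comes without alpha, power, effect size, SD or dropout, so the plan has no figure of its own to recover.

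**Inputs.** From the documents: n = 30 or 60 per arm, 1:1 allocation, scores at baseline and 3 months. Assumed, because the documents give none: two-sided alpha 0.05, normal scores, no dropout, correlation r = 0.5 to 0.7 between baseline and 3 months, a true difference of 0.5 SD for power, and a shared shift of 0 or ±0.2 SD. The plan does not say which Wilcoxon test it means; rank-sum is used here for d) because it fits two independent groups.

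**1. Detectable difference, 80% power.** The noncentral t gives 0.736 SD at 30 per arm and 0.516 SD at 60, unadjusted. Multiply by √(1 − r²) for baseline adjustment and by √(2(1 − r)) for change scores.

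| n per arm | r | unadjusted | change score | adjusted |
|---|---|---|---|---|
| 30 | 0.5 | 0.74 | 0.736 × 1.000 = 0.74 | 0.736 × 0.866 = 0.64 |
| 30 | 0.7 | 0.74 | 0.736 × 0.775 = 0.57 | 0.736 × 0.714 = 0.53 |
| 60 | 0.5 | 0.52 | 0.516 × 1.000 = 0.52 | 0.516 × 0.866 = 0.45 |
| 60 | 0.7 | 0.52 | 0.516 × 0.775 = 0.40 | 0.516 × 0.714 = 0.37 |

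At r = 0.3 and 30 per arm, adjustment gains little (0.736 × 0.954 = 0.70 SD), and change scores do worse than no adjustment (0.736 × 1.183 = 0.87 SD).

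**2. Power for 0.5 SD** (20,000 simulated trials per setting; ranges are over r = 0.5 to 0.7).

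| n per arm | rank-sum, raw | rank-sum, change | rank ANCOVA | ANCOVA |
|---|---|---|---|---|
| 30 | 45-46% | 46-67% | 56-71% | 59-75% |
| 60 | 75% | 75-93% | 85-95% | 88-97% |

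All four keep a type I error of 4.7-5.2%.

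**3. Chance imbalance.** The probability that the arms differ at baseline by more than 0.3 SD is 2(1 − Φ(0.3/√(2/n))). At n = 30 this is 2(1 − Φ(1.16)), about 25%. At n = 60 it is 2(1 − Φ(1.64)), about 10%. An unadjusted 3-month comparison does not correct for it.

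**4. Correlation test.** Power is approximately Φ(atanh(r)·√(n − 3) − 1.96). At n = 30, r = 0.5: 0.549 × 5.196 − 1.96 = 0.89, giving 81%. At r = 0.7: 0.867 × 5.196 − 1.96 = 2.55, giving 99%. At n = 60 it is 98.6% or more. Simulated at n = 30, it is significant in 83-99% of trials with no GENIE effect and in 83-99% with a 0.5 SD effect. It does not discriminate.

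**5. Pre/post test in the GENIE arm when GENIE has no effect** (signed-rank, 40,000 simulated trials per setting; share significant in the favourable direction).

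| shared change in both arms | n = 30 | n = 60 |
|---|---|---|
| none | about 2.5% | about 2.5% |
| improve by 0.2 SD | 17-26% | 32-48% |
| worsen by 0.2 SD | 0.14% or less | 0.02% or less |

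The between-arm rank-sum test stays at 2.3-2.6% favourable throughout.

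**The case against.** The best counter-argument is that items a)/b) and c)/d) run in parallel. Item b) is a between-group comparison of pre and post, so d), with its cross-reference, may already mean a comparison of change. That would use baseline, and at 30 per arm the detectable difference would improve only from 0.74 to 0.64 SD (r = 0.5) or from 0.57 to 0.53 SD (r = 0.7). This stands as a limit on the size of the gain. It also confirms that the text does not settle the matter.

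The correlation may be loose wording for a comparison, since the matching 12-month item uses a verb of comparison. That is possible, but the text as written asks for a correlation with a significance test. If a comparison was meant, it is another pre/post test and still does not estimate the treatment contrast.

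The objective and Analysis of Outcomes do point to the between-arm comparison, and any harm from c) is hypothetical. That is fair, but neither place ranks the listed tests. Five sections are announced and four lettered items follow; the gap does not supply a ranking.

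The most useful objection is that ANCOVA leans on normality while the plan chose rank tests. With skewed scores at 30 per arm, the result for plain ANCOVA is mixed. Under one lognormal set-up (r = 0.5, mean difference 0.5 SD), power moved from 68% for raw rank-sum to 74% with moderate skew, and from 92% to 88% with strong skew. Under another it fell from 72% to 61% and from 94% to 65%. Rank ANCOVA gained in all four cases (79%, 97%, 83% and 98%). The case for using baseline therefore survives, but the form of the model matters.

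**Conclusion.** The concern holds and should be fixed before analysis. Item d) is planned, valid and controls type I error. The plan does not say whether it uses baseline, and does not make it the decisive clinical result. Neither test in item c) estimates GENIE versus usual care.

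If d) is a raw 3-month comparison, adjustment raises power for a 0.5 SD difference by roughly 10 to 30 percentage points at 30 per arm (46% to 56% for rank ANCOVA at r = 0.5; 46% to 75% for ANCOVA at r = 0.7). If d) means change scores, the rank-based gain is about 10 points at r = 0.5 (46% to 56%) and 4 at r = 0.7 (67% to 71%). These sizes rest on assumed normality, correlation and effect. The gain is small at r = 0.3, and plain ANCOVA can lose to the rank-sum test when scores are strongly skewed. How misleading the pre/post test could be depends on the unknown course of scores after leaving the service. That neither part of c) addresses the randomised comparison does not depend on these assumptions.

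**What to change.** Name one primary clinical analysis: 3-month CAT by randomised arm, adjusted for baseline CAT, reported as an estimate with a 95% confidence interval. Fix the form in advance: ANCOVA, or a baseline-adjusted rank or ordinal model if ranks are preferred or marked skew is expected. Use the same model for GAD-7 and PHQ-9. Report within-arm changes descriptively, without p-values, and delete the correlation test. If any Wilcoxon test is kept, say whether it is signed-rank or rank-sum.

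The cost is analysis-plan wording; no new data or visits are needed. The drawbacks are a residual check if ANCOVA is chosen, and that the model needs both the baseline and the 3-month score for each participant.
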